validated questionnaire administered biweekly. Analysis included 62 children, mean (SD) age 9.9 (3.9) years, 32 (52%) females, predominantly HbSS (87%), with mean baseline 25-hydroxyvitamin D of 14.3 ng/mL. The mean (SEM) 25-hydroxyvitamin D concentrations during Treatment Years 1 and 2 are shown in Figure 2. A total of 291 adverse events were reported, including 55 serious adverse events in 20 subjects, most of which were expected for sickle cell disease; none were attributed to the study drug. There were 17 abnormal safety laboratory values; all abnormal laboratory values were determined to be clinically insignificant, without requiring withholding or discontinuation of study treatment.

The annual rates of respiratory events at baseline, intervention year-1, and year-2 with the high-dose were 4.34 ± 0.35 (SEM), 4.28 ± 0.36 , and 1.49 ± 0.37 , and, with the standard-dose, 3.91 ± 0.35 , 3.34 ± 0.37 , and 1.54 ± 0.37 , respectively (see Figure 1 above). In pediatric patients with sickle cell disease, two-year monthly oral vitamin D3 was associated with a >50% reduction in the rate of respiratory illness during the second year, with similar decreases from high- and standard-dose treatment.

In summary, in children and adolescents with sickle cell disease who received monthly bolus doses of oral vitamin D₃ under observation for two years, the annual rates of respiratory events (respiratory infections, asthma exacerbations and acute chest syndrome) decreased by more than 50% during the second year of treatment, with similar reductions in the groups treated with 100,000 IU/month and with 12,000 IU/month. The treatment groups did not differ significantly with respect to pulmonary function, hand-grip strength, fever or episodes of vaso-occlusive pain. Both doses were safe with no significant differences in adverse events.

[figure not shown]

Figure 2: Mean serum 25-hydroxyvitamin D concentrations by treatment group: High-dose: 100,000 IU (2.5 mg) vitamin D₃ given once a month under observation (daily equivalent 3,333 IU/day); Standard-dose, 12,000 IU (0.3 mg) vitamin D₃ given once a month under observation (daily equivalent 400 IU/day).

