Prior to initiation of treatment, subjects will have baseline assessments that will include: (i) pulmonary function test (limited to age above 5y/o); and (ii) blood tests for biomarkers of inflammation (complete blood count, C-reactive protein, and Th1/Th2 cytokines). Participants will be seen monthly in person or remotely in a telehealth visit for confirmation of administration of study drug, accounting of unused study drug, interval history including respiratory events and adverse event monitoring. Laboratory safety assessments will include serum albumin-corrected calcium and spot urinary calcium-creatinine ratios to be obtained immediately before study drug administration, and performed at intervals as shown in the Table (Schedule of Study Evaluations) to monitor hypercalcemia and hypercalcuria. Abnormal laboratory values will be reviewed by the Clinical Trial Safety Officer to determine clinical significance and need for intervention, as described in detail below.

Daily vitamin D for prevention of respiratory complications in sickle cell disease

[figure not shown]

Figure: Profile of the Phase 2 ViDAS-2 clinical trial design.

Blood specimens for 25(OH)D and vitamin D₃ will be collected every third month for the first six months, then at months 6, 12, 18 and 24, stored at -112°F (-80°C) freezer, and analyzed in a single batch at the end of the study by Ultra Performance Liquid Chromatography-Tandem Mass Spectrometry (See *below* for Vitamin D assay). Adverse events will be determined according to the Common Terminology Criteria of Adverse Events version 4.0. Pulmonary function tests will be repeated at 12-months and 24-months after initiation of treatment, while the biomarkers of inflammation, the health-related quality of life questionnaire and the Block Calcium and Vitamin D screener and sun exposure questionnaires will be collected every 6 months. Table 3 below outlines the schedule of study evaluations.

Primary Outcome Measure: Respiratory Events

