deviation or as counts and proportions. Study Group differences in continuous measures at baseline will be compared using independent *t* tests and differences in dichotomous categorical measures at baseline will be compared using Fisher's exact test.

Sample size

For sample size estimation, we base our estimate of the annual rate of respiratory events on the rate observed in the earlier ViDAS-1 trial in our study population, a mean annual baseline respiratory event rate of 4.1. For our estimate of the treatment effect, we use the observed reduction in annual mean respiratory event rate in the earlier ViDAS-1 trial for *monthly* bolus oral vitamin D3, 100,000 IU/mo (2.5 mg/mo), from Treatment Year 1 to Treatment Year 2 from 4.28 ± 0.36 (SEM) to 1.49 ± 0.37 , or a decrease of about 65 percent. Using a conservative estimate of a treatment effect of 50 percent reduction in the rate of respiratory events as the minimal *clinically* significant difference to be detected, **26 subjects in each group will be sufficient to detect an effect size of this magnitude with a two-sided significance level of alpha = 0.025 and 90 percent power. Allowing for as much as a 15 percent loss of participants during the two-year study (due to clinical events, such as initiating chronic red blood cell transfusion therapy, failure of compliance or exclusion or withdrawal for any reason), then our sample size estimate is $26/0.85 = 31$ participants in each treatment group, or a total of 62 participants.** Although the secondary analyses planned have not entered into the calculation of the sample size required for the proposed study, the conservative specification for the treatment effect; 90 percent power; and a generous allowance for loss of participants, should help provide adequate power for subsidiary comparisons.

Annualized Event Rate and Inter-Event-Interval (IEI)

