All primary and secondary outcome analyses will be performed under the intent-to-treat principle. Crude estimates of group differences in the annualized event rate and average inter-event-interval during Treatment Year 1 and Treatment Year 2 will be analyzed by linear mixed models for repeated measures with fixed effects for group, time and group-by-time interaction, and an AR(1) covariance structure. Analyses of secondary outcomes for pulmonary function testing will also use this approach. Further analysis of treatment group differences will be assessed using a variation of the Cox Proportional Hazards model with a counting process input of start and stop times for each event and the robust sandwich covariance estimator of Lin.⁶³ This approach models hazard for recurrence under the assumption of proportional mean processes and generates hazard ratios with 95% confidence intervals and Wald Chi-Square statistics for testing the null hypothesis. We will evaluate the influence of the event rate, average IEI as covariates and calculate between treatment group hazard ratios. We will also evaluate the influence of randomization stratifying variables as covariates of the estimate of the between treatment group difference: sex (female vs male), age (child vs adolescent) and hydroxyurea use (use vs non-use). For participants in each treatment group who withdraw from the study prior to completion of the protocol, we will repeat the primary intent-to-treat analysis with the subset of participants who completed the two-year study in a "per protocol" analysis. Finally, treatment group differences in adverse events of least grade 2 severity will be assessed with chi-square or Fisher's Exact test. We will only present comparisons of events where three or more instances are reported over the two-year treatment period.

DATA AND SAFETY MONITORING

Adherence to protocol: Conduct of the clinical trial will be in accordance with this new protocol for the ViDAS-2 study in our Investigational New Drug application. This protocol includes the appointment of a Clinical Trial Safety Officer to review laboratory results as they become available, and the formation of a Data and Safety Monitoring

Board (DSMB) consisting of an expert in pediatric sickle cell disease, a biostatistician, and a Pediatric Endocrinologist with expertise in vitamin D metabolism. The DSMB will meet bi-annually.

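### The only formal between-arm safety analysis is a significance test without an estimate or interval, so a non-significant result cannot by itself support a conclusion of equal safety

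*Combined protocol and SAP*

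**What the plan says.** Under Treatment Outcome Analysis in the SAP, "treatment group differences in adverse events of least grade 2 severity will be assessed with chi-square or Fisher's Exact test". The next sentence limits what is shown: "We will only present comparisons of events where three or more instances are reported over the two-year treatment period". No effect measure, confidence interval, margin or significance level is given for these tests, and the section does not say whether the unit is the child or the event. Earlier in the same section, the efficacy hazard ratios are to be given with 95% confidence intervals.

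The Sample size section rests on respiratory events alone. It starts from "a mean annual baseline respiratory event rate of 4.1" and a 50% reduction, and states that "26 subjects in each group will be sufficient to detect an effect size of this magnitude" at a "two-sided significance level of alpha = 0.025 and 90 percent power". Allowing for 15% loss, this becomes 31 per group and 62 in total. The section also says that secondary analyses did not enter the calculation. Subject Justification gives a different figure, about 80 enrolled.

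Section 6a (Study protocol) adds laboratory monitoring: "Laboratory safety assessments will include serum albumin-corrected calcium and spot urinary calcium-creatinine ratios", drawn immediately before dosing. No comparison of these values between arms is specified. The linear mixed model in Treatment Outcome Analysis is assigned to event rate, inter-event interval and pulmonary function.

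The ViDAS-1 summary in section 4 (General investigational plan), for a trial of 31 against 31, closes with: "Both doses were safe with no significant differences in adverse events".

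**The concern.** A test against no difference answers only whether the data rule out equality. When it is not significant, it does not say how large an excess of harm remains compatible with the data, and with about 31 children per arm that excess can be large. Sustained circulating vitamin D3 is the new feature of the daily arm, so how its safety compares with monthly dosing is a real question. If only the test is reported, a reader cannot tell evidence of similar safety from lack of information.

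The ViDAS-1 sentence shows how easily the two are put together: a statement that the doses were safe stands beside a statement that no significant difference was found, in a trial of the same size.

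**Working it through.** **1. The plan's own figure.** The Sample size section gives neither a standard deviation nor a formula. Taking SD = SEM × √31 from the ViDAS-1 high-dose rates (SEM 0.36 and 0.37) gives SD = 2.00 and 2.06. The difference is 4.1 × 0.5 = 2.05 events per year. For two means, at two-sided 0.025 and 90% power:

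n = 2 × [(2.241 + 1.282) × SD / 2.05]²

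This is 25.07, rounded up to 26, for SD 2.06. For SD 2.00 it is 23.7, rounded up to 24 (26 with the t distribution). Then 26/0.85 = 30.6, rounded up to 31. The stated 26 and 31 are reproduced, and they concern efficacy only. The plan has no safety power or precision figure to reproduce.

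**2. Inputs for the safety check.**
- Children per arm: 31 planned and 26 after loss (Sample size); 40 if all of about 80 are randomized equally (Subject Justification).
- Base risk: 20/62 = 32.3% of children with a serious adverse event in ViDAS-1, both doses pooled (section 4). The documents give no other per-child frequency, so 20%, 10% and 5% are assumptions chosen to show a range.
- Significance level: two-sided 0.05, assumed. Using the efficacy level of 0.025 would raise every miss rate below.

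**3. Chance of missing a true doubling.** With a events among n children in one arm and b among n in the other, a ~ Bin(n, p) and b ~ Bin(n, 2p). The miss rate is 1 minus the sum, over all 2×2 tables with p-value ≤ 0.05, of Pr(a) × Pr(b). Each cell shows Fisher / uncorrected chi-square.

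| Base risk to doubled risk | 26 per arm | 31 per arm | 40 per arm |
|---|---|---|---|
| 32.3% to 64.5% | 46% / 36% | 34% / 25% | 21% / 15% |
| 20% to 40% | 75% / 63% | 69% / 59% | 59% / 50% |
| 10% to 20% | 91% / 82% | 90% / 80% | 84% / 75% |
| 5% to 10% | 98% / 91% | 98% / 89% | 96% / 85% |

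The result depends strongly on base risk. At 31 per arm, a doubling from 40% to 80% is missed only 13% / 8% of the time, and one from 2% to 4% at least 98% of the time.

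**4. What an interval would show that the test does not.** Two illustrative results at 31 per arm, with Newcombe 95% intervals built from the Wilson limits of each proportion:
- 8/31 against 3/31: Fisher p = 0.18. Wilson limits are 13.7% to 43.2% and 3.3% to 24.9%. The difference is 16.1 points. Lower limit: 0.161 − √[(0.258 − 0.137)² + (0.249 − 0.097)²] = −0.03. Upper limit: 0.161 + √[(0.432 − 0.258)² + (0.097 − 0.033)²] = +0.35.
- 10/31 against 10/31: difference 0, interval −22 to +22 points.

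Both are non-significant. The first leaves an excess of up to 35 points unexcluded and the second 22 points. The p-value shows neither.

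**The case against.** Three stronger readings are tempting, and the documents do not support them.

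- *Safety is judged only by these tests.* This is true of the formal between-arm comparison, not of safety as a whole. Data and Safety Monitoring provides for a Clinical Trial Safety Officer who reviews laboratory results as they arrive, weekly calls in the first month, tiered reporting of serious events, and DSMB reviews at least twice a year. These look for abnormalities and safety signals as they arise; no estimate of the difference between arms is described there.
- *A non-significant result will be read as safe.* No ViDAS-2 text says so. The ViDAS-1 summary did not rest on a p-value alone either: most serious events were expected for the disease, none was attributed to study drug, and all 17 abnormal safety laboratory values were judged clinically insignificant. The pairing of the two statements makes the misreading plausible, but it is not a rule of this plan.
- *The tests will very likely be non-significant even if harm doubles.* At the one documented base risk, 32%, a doubling is detected 66% (Fisher) to 75% (chi-square) of the time at 31 per arm. The high miss rates belong to assumed base risks of 20% and below.

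It is also fair to say that low power for adverse events is ordinary in a Phase 2 trial sized for efficacy, and that the plan discloses that secondary analyses were not powered. The two arms deliver roughly equal monthly amounts of vitamin D, so the documents do not tie a doubling of all-cause serious events to a mechanism; the doubling is a yardstick here, not a forecast.

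The calcium comparison has a limit of its own. Samples are drawn just before dosing, which in the monthly arm is about a month after the bolus. Section 4 says that vitamin D3 is near baseline in under a week after 100,000 IU. The comparison therefore sets pre-bolus values against daily steady state and cannot see a post-bolus rise.

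What stands against all this is the form of the analysis. Intervals could be worked out later from counts of affected children, but the plan commits neither to those counts nor to the intervals, although it commits to intervals for efficacy.

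**Conclusion.** The point holds as one about analysis and reporting, and the change should be made. A chi-square or Fisher test alone is too weak a basis for any statement that daily and monthly dosing are equally safe. At 31 per arm it misses a doubling 34% to 98% of the time with Fisher's test, and 25% to 89% with the uncorrected chi-square, for base risks from 32% down to 5%. At 40 per arm the ranges are 21% to 96% and 15% to 85%.

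These figures rest on a two-sided 0.05 level that the plan does not state, on one row per child, and on assumed base risks except for the 32%, which is itself for serious events pooled over both ViDAS-1 doses and not for events of grade 2 or above. The sample size is not at fault, and nothing here suggests that safety oversight during the trial is missing.

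**What to change.** In Treatment Outcome Analysis, replace the test-only comparison:

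1. For each adverse event, and for any serious adverse event, report the number of children affected in each arm and the risk difference, daily minus monthly, with a 95% Newcombe or exact interval. State that the comparative safety conclusion is worded from the interval and that a non-significant p-value is not taken as evidence of equal safety.
2. As a supporting analysis, compare albumin-corrected calcium and log urinary calcium/creatinine between arms as repeated measures, adjusted for the pre-treatment value, with 95% intervals. State that samples are pre-dose, so the comparison does not capture any post-bolus rise in the monthly arm.

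The cost is SAP wording and a little more analysis of data already being collected, with no new participants or procedures. The fix adds no power to the adverse-event comparison; it makes the remaining uncertainty visible. The safety statement will read less favourably, for example that an excess of about 20 points is not excluded.

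### The adverse-event rule (grade 2 or higher, three or more instances) could leave one or two cases of a monitored toxicity out of the by-arm safety report

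*Combined protocol and SAP*

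**What the plan says.** The last part of the Treatment Outcome Analysis section of the Statistical Analysis Plan sets two limits on the comparison of adverse events:

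- Severity: "treatment group differences in adverse events of least grade 2 severity will be assessed with chi-square or Fisher's Exact test".
- Frequency: "We will only present comparisons of events where three or more instances are reported over the two-year treatment period".

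Neither limit carries an exception. The plan does not define an instance as an event or as an affected participant, nor say whether the three are counted within an arm or over both arms. No other by-arm summary of adverse events or safety laboratory values is specified.

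Section 6a (Study protocol) schedules serum albumin-corrected calcium and spot urinary calcium/creatinine ratios through the trial "to monitor hypercalcemia and hypercalcuria". The Sample size section gives 31 "participants in each treatment group, or a total of 62 participants".

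**The concern.** The trial repeatedly measures two laboratory markers of vitamin D toxicity in children, but the analysis plan does not commit to showing the results by arm. If one or two children in one arm developed hypercalcemia and none did in the other, the rule as worded would not require that split to appear. Abnormalities below grade 2 would not be compared at any count.

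The undefined unit makes the rule erratic. Counted as events, three episodes in one child qualify, while one episode in each of two children does not. The distinction matters in this population: section 4 (General investigational plan) reports 55 serious adverse events in 20 subjects in the earlier trial, or 55/20 = 2.75 per affected child. Chi-square and Fisher's exact tests also need each child counted once, which the plan does not state.

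At stake is how complete the safety report is for a comparison of two dosing schedules, where their relative safety is a natural question.

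**Working it through.** **Denominator.** The Sample size section states that "26 subjects in each group will be sufficient to detect an effect size of this magnitude". The design uses a two-sided alpha of 0.025 and 90% power. No standard deviation is given. From the larger quoted standard error, SD = 0.37 × √31 = 2.06, and the difference to detect is 50% of 4.1 = 2.05 events per year. The two-means formula gives n = 2 × (2.241 + 1.282)² × 2.06² / 2.05² ≈ 25.1, which rounds up to 26. With the stated 15% loss, 26/0.85 = 30.6, so 31 per arm and 62 in total. The plan's figure is reproduced.

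**Assumptions for the threshold.** The documents give no toxicity rate, so a range is used. The toxicity is taken to occur in one arm only, at most once per child, at grade 2 or higher, with n = 31 and X ~ Binomial(31, p). No comparison is presented when X ≤ 2. One or more cases exist but are not compared when X is 1 or 2.

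At p = 3%:

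- P(X = 0) = 0.97³¹ = 0.389
- P(X = 1) = 31 × 0.03 × 0.97³⁰ = 0.373
- P(X = 2) = 465 × 0.03² × 0.97²⁹ = 0.173
- P(X ≤ 2) = 0.935, and P(X = 1 or 2) = 0.546

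| Assumed incidence in one arm | No comparison presented, P(X ≤ 2) | One or two cases occur, not compared |
|---|---|---|
| 1% | 99.6% | 26% |
| 2% | 97.6% | 44% |
| 3% | 93.5% | 55% |
| 5% | 79.9% | 60% |
| 8% | 54.4% | 47% |
| 10% | 38.9% | 35% |

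A comparison becomes as likely as not only at an incidence of about 8.5%.

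**Sensitivity to sample size.** At 5%, the chance of no comparison is 86% with 26 per arm. It is 68% with 40 per arm, the most that the enrolment of about 80 in Subject Justification would allow.

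**Sensitivity to the one-arm pattern.** If both arms carry the risk and instances are pooled over 62 children, the chance of two or fewer cases is 71.5% at 3% and 39.5% at 5%. Subtracting the chance of none (0.97⁶² = 0.151; 0.95⁶² = 0.042), one or two cases occur and go uncompared with probability 56% and 35%.

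**Is any significant test lost?** For x cases against 0 with 31 per arm, the two-sided Fisher p-value is 2 × C(31,x)/C(62,x). No significance level is stated for adverse events, so 0.05 is assumed.

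- 1 v 0: p = 1.00
- 2 v 0: 2 × 465/1,891 = 0.49
- 3 v 0: p = 0.24
- 4 v 0: p = 0.11
- 5 v 0: p = 0.053
- 6 v 0: p = 0.024

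Six against none is the smallest split against zero below 0.05, so none is lost.

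**What by-arm counts would add.** One of 31 is 3.2% (exact 95% interval 0.1% to 16.7%), and two of 31 is 6.5% (0.8% to 21.4%). These intervals tell a reader how large a risk remains compatible with the data; a p-value of 0.49 does not.

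The severity limit cannot be sized. Section 4 reports 17 abnormal safety laboratory values in the earlier trial, all judged clinically insignificant, but gives neither their grade nor how many concerned calcium.

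**The case against.** The strongest reply is that the sentence restricts comparisons, and that it directly follows the sentence defining those comparisons as chi-square or Fisher tests. On that reading it limits only which tests are reported, and rarer events could still be tabulated. The Statistical Analysis Plan also says in general terms that data will be summarized as counts and proportions. This reading is possible, and nothing in the plan says that rarer events go unlisted. But the text does not secure it: the general sentence does not name adverse events, and no by-arm adverse-event table is promised.

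Second, individual cases do not depend on this rule. Under Data and Safety Monitoring, the Safety Officer reviews laboratory results as they are performed, and abnormalities needing intervention go immediately to the Sponsor-Investigator. Serious events reach the DSMB within a week or quarterly, and other events at its biannual review. This stands in full: a reader might infer that a toxicity could pass unnoticed, and the documents do not support that. These routes do not supply a comparison of the arms, however, and the annual DSMB report is presented blinded.

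Third, the one-arm pattern is an assumption. The protocol describes the two schedules as delivering about the same monthly amount, and if both arms carry the risk, the omission probabilities at 5% fall markedly. With calcium measured repeatedly, counting recurrent episodes as instances would lower them further. This also stands, so the tabulated percentages illustrate and do not predict.

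**Conclusion.** The concern holds as a gap in descriptive by-arm safety reporting. With 31 per arm and a one-arm toxicity affecting 1% to 5% of children, at most once each, the chance that one or two cases occur and no comparison is presented is 26% to 60%. The chance of two or fewer cases is 93% at 3% and 80% at 5%, or about 72% and 40% if both arms carry the risk and counts are pooled over 62. All of these rates are assumed.

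A reader might go further and infer that the rule hides a real treatment difference. The documents do not support that: two cases against none cannot be told from chance at this size, and no comparison that could reach significance is suppressed. Nor does the rule affect the primary analysis. It should still be changed, because tests on so few events say little, which makes counts and intervals by arm the useful output, and the plan does not commit to them.

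**What to change.** Replace the final sentence of Treatment Outcome Analysis so that it provides for the following:

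1. Adverse events are tabulated by arm, giving the number of participants affected and the number of events.
2. Serious events, and abnormalities of serum calcium and urinary calcium/creatinine, are always shown by arm whatever their grade or count, with exact confidence intervals for the proportion of participants affected.
3. The threshold applies to p-values only and is defined as three or more participants, each counted once per event type. State whether the three are counted per arm or over both arms.

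The cost is one longer table and a few lines of plan wording. Data collection, monitoring and sample size are unchanged.

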Safety monitoring and review plan: For the first month after initiation of study treatment, the Clinical Research Coordinator will telephone each study participant (or their parent or guardian) weekly to ask about any adverse experiences or any change from baseline status. To maintain blinding of participant treatment assignment during safety monitoring, a Clinical Trial Safety Officer, a physician expert in Pediatric Endocrinology and vitamin D metabolism, will be appointed to review laboratory results as they are performed during the course of the clinical trial to detect any abnormality requiring intervention. Abnormalities that require dose adjustment or other intervention will be reported immediately to the Sponsor-Investigator and summarized for annual reports to the U.S. Food and Drug Administration (FDA), the DSMB, and the Columbia University Institutional Review Board (CU IRB).

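### Serial serum calcium and urinary calcium/creatinine are collected in every child as toxicity measures, but the plan specifies no between-arm analysis of either

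*Combined protocol and SAP*

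**What the plan says.** Section 6a (Study protocol) states that "Laboratory safety assessments will include serum albumin-corrected calcium and spot urinary calcium-creatinine ratios to be obtained immediately before study drug administration", at intervals set out in the schedule table, "to monitor hypercalcemia and hypercalcuria". As extracted, the schedule shows 7 marks for serum calcium and 13 for urinary calcium/creatinine, counting those before treatment; columns may be displaced.

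Two uses are given for the results. Section 6a says "Abnormal laboratory values will be reviewed by the Clinical Trial Safety Officer to determine clinical significance and need for intervention". The Safety monitoring and review plan has the Safety Officer "review laboratory results as they are performed during the course of the clinical trial to detect any abnormality requiring intervention", with abnormalities that call for intervention reported at once to the Sponsor-Investigator and summarised annually for the FDA, the DSMB and the IRB.

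The SAP names neither measure. Its subsidiary hypotheses cover pulmonary function, airway inflammation and the immune system. Under Treatment Outcome Analysis the repeated-measures mixed model is applied to the event rate, the inter-event interval and pulmonary function. The one between-arm safety analysis is there too: "treatment group differences in adverse events of least grade 2 severity will be assessed with chi-square or Fisher's Exact test", presented only for events with three or more instances over two years.

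**The concern.** The trial compares two schedules that deliver about the same amount of vitamin D per month. Serum and urinary calcium are the protocol's own toxicity measures, taken serially in every child. Blinded, child-by-child review can protect an individual but does not compare the arms. A shift in calcium handling that stays mostly within the reference range would trigger no individual action and would enter no planned table.

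The adverse-event comparison is an uncertain substitute, because nothing says that an abnormal calcium value becomes an adverse event. For ViDAS-1, section 4 gives 291 adverse events and, as a separate count, 17 abnormal safety laboratory values, and says "all abnormal laboratory values were determined to be clinically insignificant". If values here are judged in the same way and not coded, the planned safety comparison carries no information from them. At stake is how completely the safety of the two schedules is described. No efficacy conclusion depends on it.

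**Working it through.** **The plan's own figures.** No figure is given for calcium, which did not enter the sample size. The stated size does reproduce and supplies the arm sizes used below. The SD is 0.37 × √31 = 2.06 and the difference is 0.5 × 4.1 = 2.05. Then n = 2 × (2.241 + 1.282)² × (2.06/2.05)² = 25.1, so 26 per arm, and 26/0.85 = 30.6, so 31. (Subject Justification speaks of about 80 enrolled; the 62 of the sample-size section is used here.)

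**Assumptions.** The documents give no SD, reference limit, within-child correlation or clinically relevant shift for either measure. Values are therefore taken as normal, in SD units, with exchangeable correlation ρ of 0.3 to 0.7, one pre-treatment value and two-sided 0.05. On-treatment values number m = 5 for serum calcium (7 marks less screening and randomization) and about m = 12 for the urinary ratio (13 less screening).

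**Direct comparison.** The child's on-treatment mean, adjusted for the pre-treatment value, has residual variance v = [1 + (m − 1)ρ]/m − ρ². Approximate power is Φ(d/√v × √(n/2) − 1.96) for a shift of d SD. For m = 5:

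- ρ = 0.3: v = 0.44 − 0.09 = 0.35.
- ρ = 0.5: v = 0.60 − 0.25 = 0.35.
- ρ = 0.7: v = 0.76 − 0.49 = 0.27.

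With n = 31 and d = 0.4:

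- v = 0.35: 0.4/0.592 × 3.937 = 2.66, power Φ(0.70) = 76%.
- v = 0.27: 0.4/0.520 × 3.937 = 3.03, power Φ(1.07) = 86%.

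Simulation, which allows for the t distribution and carries Monte Carlo error, gives about 71-84%. The 95% confidence interval has half-width 1.96 × √v × √(2/31), which is 0.26 SD (v = 0.27) to 0.29 SD (v = 0.35).

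**Threshold route.** Suppose every value above a cut-off were coded as an adverse event and children with any such value were compared by Fisher's exact test. Simulated power beside the direct comparison:

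| Setting | Shift | Baseline-adjusted comparison | Fisher, 97.5th percentile | Fisher, 99.5th percentile |
|---|---|---|---|---|
| 5 values, 31 per arm | 0.4 SD | 71-84% | 7-15% | under 2% |
| 5 values, 26 per arm | 0.4 SD | 65-79% | at most about 12% | under 2% |
| 12 values, 31 per arm | 0.4 SD | 83-88% | 12-26% | 1-6% |
| 12 values, 31 per arm | 0.5 SD | not tabulated | 19-41% | 2-11% |

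**What the count comparison needs.** With 31 per arm, the two-sided Fisher p-value for k children against none is 2 × C(31,k)/C(62,k):

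- k = 3: 2 × 4,495/37,820 = 0.24.
- k = 5: 2 × 169,911/6,471,002 = 0.053.
- k = 6: 2 × 736,281/61,474,519 = 0.024.

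Six affected children against none is the smallest such split that reaches 0.05.

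**The case against.** A reader might infer that a calcium shift would leave no trace. The documents do not support that. Under Records to be kept, the results of all laboratory assessments go onto case report forms and into a database, so an unplanned tabulation stays possible. Abnormalities needing intervention reach the FDA, the DSMB and the IRB. The DSMB includes a biostatistician and a pediatric endocrinologist and reviews safety twice a year. A marked imbalance coded at grade 2 or more could also surface in the planned test. What is missing is a pre-specified comparison.

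A reader might also infer that the two schedules will be declared equally safe. No such claim is planned, and section 4 reports the abnormal laboratory count for ViDAS-1 separately, which suggests that the team does look at these data. Nor do the documents show that the adverse-event comparison will hold no laboratory information. They are silent on coding, and section 4 ties clinical insignificance to not withholding or stopping treatment, without saying how such values were counted.

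Two further objections stand. The monitoring aim is a threshold question, and a 0.4 SD mean shift is not shown to be harmful. The direct comparison also has limits: for a 0.2 SD shift with five values and 31 per arm its power is only about 25-31%, and pre-dose sampling means it cannot see the days after a monthly dose. These points lower the weight of the finding. They do not supply the missing comparison.

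**Conclusion.** The gap is real and minor. Followed as written, the plan compares its own toxicity measures between arms only through a threshold test on adverse events, if at all. Distributional shifts would not appear in the planned results. Nor would abnormalities that are uncoded, below grade 2 or fewer than three.

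The ordering of the two approaches holds in every setting tried, including 26 per arm after the planned 15% loss, but the sizes rest on the assumed correlation, normality, cut-offs and shift. A claim that the threshold route always detects under 2% at a high cut-off would be too strong: with about 12 urinary values at the 99.5th percentile it reaches about 6% for a 0.4 SD shift and 11% for 0.5 SD.

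**What to change.** In the SAP, under Treatment Outcome Analysis, add text to this effect:

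> Albumin-corrected serum calcium and log-transformed urinary calcium/creatinine will be compared between arms with the repeated-measures mixed model already specified, adjusted for the pre-treatment value. The difference and its 95% confidence interval will be reported as a secondary safety estimate. The number of children with any value above the laboratory's reference limit will be tabulated by arm, whatever the judged clinical significance and without the three-instance rule. All samples are pre-dose; they do not describe the days after a monthly dose and cannot support a claim of equal safety.

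The SAP should also state whether abnormal laboratory values are coded as adverse events, so that the existing comparison can be interpreted.

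The cost is a few sentences and one extra table from data already collected. There are no new samples, no change to treatment or monitoring rules, and no effect on the primary analysis or the sample size. The downside is one more secondary estimate that needs cautious reading, since its confidence interval is wide enough to include small shifts.
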